**Table 2: Classification of Adverse Events by Intensity**

**Grade 1: MILD:** An event that is easily tolerated by the subject, causing minimal discomfort and not interfering with everyday activities.

**Grade 2: MODERATE:** An event that is sufficiently discomforting to interfere with normal everyday activities.

**Grade 3: SEVERE:** An event that prevents normal everyday activities.

**Grade 4: LIFE THREATENING:** An event that requires urgent intervention.

**Grade 5: DEATH:** An event that is related to death.

**Table 3: Classification of Adverse Events by Relationship to Study Drug**

**UNRELATED:** This category applies to those AEs that are clearly and incontrovertibly due to extraneous causes (disease, environment, etc.).

**UNLIKELY:** This category applies to those AEs that are judged to be unrelated to the test drug, but for which no extraneous cause may be found. An AE may be considered unlikely to be related to study drug if or when it meets 2 of the following criteria: (1) it does not follow a reasonable temporal sequence from administration of the test drug; (2) it could readily have been produced by the subject's clinical state, environmental or toxic factors, or other modes of therapy administered to the subject; (3) it does not follow a known pattern of response to the test drug; or (4) it does not reappear or worsen when the drug is re-administered.

**POSSIBLY:** This category applies to those AEs for which a connection with the test drug administration appears unlikely but cannot be ruled out with certainty. An AE may be considered possibly related if or when it meets 2 of the following criteria: (1) it follows a reasonable temporal sequence from administration of the drug; (2) it could not readily have been produced by the subject's clinical state, environmental or toxic factors, or other modes of therapy administered to the subject; or (3) it follows a known pattern of response to the test drug.

**PROBABLY:** This category applies to those AEs that the investigator feels with a high degree of certainty are related to the test drug. An AE may be considered probably related if or when it meets 3 of the following criteria: (1) it follows a reasonable temporal sequence

from administration of the drug; (2) it could not be reasonably explained by the known characteristics of the subject's clinical state, environmental or toxic factors, or other modes of therapy administered to the subject; (3) it disappears or decreases on cessation or reduction in dose (note that there are exceptions when an AE does not disappear upon discontinuation of the drug, yet drug-relatedness clearly exists; for example, as in bone marrow depression, fixed drug eruptions, or tardive dyskinesia); or (4) it follows a known pattern of response to the test drug.

**DEFINITELY:** This category applies to those AEs that the investigator feels are incontrovertibly related to test drug. An AE may be assigned an attribution of definitely related if or when it meets all of the following criteria: (1) it follows a reasonable temporal sequence from administration of the drug; (2) it could not be reasonably explained by the known characteristics of the subject's clinical state, environmental or toxic factors, or other modes of therapy administered to the subject; (3) it disappears or decreases on cessation or reduction in dose and recurs with re-exposure to drug (if rechallenge occurs); and (4) it follows a known pattern of response to the test drug.

When changes in the intensity of an AE occur more frequently than once a day, the maximum intensity for the event should be noted. If the intensity category changes over a number of days, then those changes should be recorded separately (with distinct onset dates).

The severity of AEs will be graded according to the National Cancer Institute Common Terminology Criteria for Adverse Events, Version 4.03 (NCI CTCAE V4.03) (Grades 1 to 5).

### 12.5.2 Serious Adverse Events

An AE is considered "serious" if it is judged by the Investigator or Sponsor to meet 1 or more of the following criteria:

- Is fatal
- Is life-threatening
- Results in subject hospitalization or prolongation of existing hospitalization
- Results in a persistent or significant incapacity or substantial disruption of the ability to conduct normal life functions
- Is a congenital anomaly/birth defect

Suzhou Kintor Pharmaceutical, Inc.  
Protocol#: GT0918-US-1002

Proxalutamide (GT0918)

- Other important medical events that may not be immediately life-threatening or result in death or hospitalization, but may jeopardize the subject and/or require medical or surgical intervention to prevent one of the outcomes listed above.

Since SAEs are critically important for identification of significant safety problems, it is important to take into account both the Investigator's and the Sponsor's assessment. If either the Sponsor or the Investigator believes that an event is serious, the event must be considered serious and evaluated by the Sponsor for expedited reporting. Hospital admission or death caused by progressive disease will not be considered an SAE and do not require expedited reporting. For such cases, initial SAE report of signs or symptoms can be made, but once final diagnosis of PD is made for the underlying cause of sign or symptom, update of SAE report is required and likely to be retracted as result.

The Investigator must notify the Ethics Review Committee/IRB of such an event in writing as soon as is practical and in accordance with international and local laws and regulations

### **12.5.3 Serious Adverse Event Reporting**

All SAEs occurring during the period between the first dose and the last dose of GT0918 or EOS must be reported to the INC Pharmacovigilance Group and will be evaluated by the medical monitor and the Sponsor. The 30-day safety follow-up "window" is set to capture possible drug-related AEs and SAE whereas unrelated SAEs should not be reported. When subject starts new therapy, the window of SAE report is closed simultaneously. All SAEs must be reported within 24 hours of occurrence or when the Investigator becomes aware of the event unless the SAE is determined not related to study drug. Notification can be made using the dedicated fax line and/or telephone line for the CRO Pharmacovigilance Group:

INC Pharmacovigilance [contact]
INC Pharmacovigilance Contact:	[contact]
CRO, Inc.:	Syneos Health (INC)
Address:	[name]
[contact]

If the Investigator contacts the INC Pharmacovigilance Group by telephone, then a written report must follow within 1 business day and is to include a full description of the event and sequelae in the format detailed in the SAE reporting form.

The event must also be recorded on the standard AE electronic CRF. Preliminary reports of SAEs must be followed by detailed descriptions later on, including clear and anonymized photocopies of hospital case reports, consultant reports, autopsy reports, and other applicable

Suzhou Kintor Pharmaceutical, Inc.  
Protocol#: GT0918-US-1002

Proxalutamide (GT0918)

documents. SAE reports must be made irrespective to whether or not the Investigator considers the event to be related to the investigational drug.

Appropriate remedial measures should be taken to treat the SAE, and the response should be recorded. Clinical, laboratory, and diagnostic measures should be employed as needed in order to determine the etiology of the problem. The Investigator must report all additional follow-up evaluations to the CRO Pharmacovigilance Group within 10 calendar days. All SAEs will be followed until the Investigator and Sponsor agree the event is satisfactorily resolved.

Any SAE that is not resolved by the end of the study or upon discontinuation of the subject's participation in the study is to be followed until it either resolves, stabilizes, returns to baseline values (if a baseline value is available), or is shown to not be attributable to the study drug or procedures.

#### **12.5.4 Overdose**

The Investigator must immediately notify the Sponsor and CRO Medical Monitor of any occurrence of overdose with study drug.

#### **12.5.5 Pregnancy**

Pregnancy occurring in the female partner of a subject participating in the study should be reported to the Investigator and the Sponsor. The reporting timeframe is from start of study drug up to 90 days after the last dose of study drug. Pregnancy is not an SAE; however, the outcome of a pregnancy must be reported to detect a potential SAE (congenital anomaly, premature birth, or birth defect). Procedures and policies at the site and at the Sponsor, regarding pregnancies, will be followed to ensure that the safety and well-being of the fetus are appropriately followed through the pregnancy to birth. In the event that a pregnancy occurs, the Investigator will then (and only then) obtain the partner's consent so that the Sponsor can hold her data on file. If the female partner is unwilling to sign the consent her data may not be held in the safety database. However, this will not affect the ability of the male subject to continue in the study.

#### **12.5.6 Safety Review and Teleconferences**

Safety review of AEs, laboratory data, concomitant medication, etc. will be performed by the study Medical Monitor on regular basis. Safety call and teleconferences will be held between the investigators/sites and medical monitor and Sponsor to discuss some important drug-related AEs and management of AEs/SAEs during the trial. The frequency may vary based on accrual and study activities.

## 13 STATISTICAL ANALYSIS

A Statistical Analysis Plan (SAP) will be prepared after the protocol is approved. This document will provide further details regarding the definition of analysis variables and analysis methodology to address all study objectives. The SAP will serve as a compliment to the protocol and supersedes it in case of differences.

The statistical evaluation will be performed using the Statistical Analysis Software (SAS®) Version 9.4 or higher (SAS Institute, Cary, NC). All data will be listed, and summary tables will be provided. Summary statistics will be presented by dose group. For continuous variables, data will be summarized with the number of subjects (N), mean, standard deviation, median, minimum, and maximum by treatment group. For categorical variables, data will be tabulated with the number and percentages of subjects for each category by treatment group. No interim analyses are planned for the Phase II dose expansion study.

### 13.1 Determination of Sample size

Phase II dose expansion stage consists of 2 arms of 30 subjects/arm, for a total of 60 subjects for Phase II. Altogether, up to 60 subjects will be estimated for the randomization and stratified by prior medication (abiraterone or enzalutamide).

Of note, the study does not allow disease progression on both abiraterone or enzalutamide. If prior treatment of one of these 2 drugs (i.e. abiraterone) only lasted less than 3 months due to toxicity, the subject (i.e. progressed on enzalutamide) is eligible and prior therapy of enzalutamide will be considered.

### 13.2 Analysis Populations

The Safety Analysis Set (SAF) will include all subjects who take at least 1 dose of study medication. Safety analyses will be conducted using the safety population.

The Full Analysis Set (FAS) will include all evaluable subjects used as the supportive analysis population for efficacy. The FAS population will be used as the primary analysis population for efficacy.

The Per Protocol (PP) Analysis Set will include all FAS subjects with the Week 12 PSA assessment and without major protocol violations.

### 13.3 Demographic and Baseline Characteristics

Data will be tabulated by #subjects (%) or Median (range) for the following variables:

Suzhou Kintor Pharmaceutical, Inc.  
Protocol#: GT0918-US-1002

Proxalutamide (GT0918)

- # Subjects
  - ◊ Age in years - median (range)
- Treatment of Primary Tumor, # (%)
  - ◊ Surgery
  - ◊ Radiation
  - ◊ No primary therapy
- Prior hormonal therapy # (%)
  - ◊ 1 line
  - ◊ 2 lines
  - ◊ 3 lines
  - ◊ >/= 4 lines
- Prior chemotherapy # (%)
  - ◊ None
  - ◊ 1 line (2 or more are excluded)

#### Clinical State of Disease

- PSA in ng/mL - median (range)
- Sites of disease # (%)
  - ◊ Bone only
  - ◊ Bone and soft tissue
  - ◊ Soft tissue only
- Soft tissue disease
  - ◊ Lymph node (LN) only
  - ◊ Visceral lesion only

- ◊ Lymph node + visceral lesion
- ◊ Other (pelvis/bladder) alone
- Prior required hormonal treatment
  - abiraterone,
  - enzalutamide

### 13.4 Efficacy Analysis

#### Assessment of Efficacy Variables:

1. Assessment of PSA: Blood samples will be collected to determine the serum total PSA concentration.
2. Change of PSA from baseline:
  - a. The percentage of change of PSA from baseline Week 12 will be calculated. Maximum percentage change of PSA from baseline at any time will be calculated.
  - b. The proportion of subjects achieving a  $\geq 50\%$  reduction in PSA at 3 months (12 weeks) as compared to baseline (study entry) will be determined.
3. Assessment of soft tissue and bone:
  - c. Soft tissue: Chest, abdomen, and pelvic CT, or MRI (if CT not possible), will be performed. Changes in the size of target lesions will be evaluated.
  - d. Bone scan: Radionuclide bone scan will be performed. Changes in the number of lesions will be reported.
  - e. Skeletal-related events: Severity of skeletal-related event (bone pain, analgesia intake) will be assessed monthly per PCWG2.
4. Symptomatic progression will be evaluated by type. Symptomatic progression is defined as evidence of unequivocal symptomatic or clinical progression defined by at least 1 of the following:
  - A marked escalation in cancer-related pain that is assessed by the Investigator to indicate the need for other systemic therapy or palliative radiotherapy. Ignore early changes ( $\leq 12$  weeks) in pain or health-related quality of life in absence of compelling evidence of disease progression. Confirm progression of pain or health-related quality of life  $\geq 3$  weeks later,

- An immediate need for initiation of new anticancer treatment, surgical or radiological intervention for complications due to tumor progression,
- A marked deterioration in ECOG performance status to Grade 3 or higher, or
- Performance status: ECOG performance status will be assessed. Changes from baseline will be evaluated.

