(AEs), or withdrawn consent. Subjects will end the study by completing the end of study (EOS) visit/assessment. The safety follow-up visit will occur 30 days after the last dose. Any subject with drug related AE or SAE will be followed until resolution or the subject's condition stabilizes, which comes first. The safety follow-up visit can be performed via phone or in clinic as required.

Disease progression will be assessed by three methods as follow over the duration of the study.

- 1) Clinical assessment
- 2) Biochemical (PSA) progression measured every 4 weeks
- 3) Radiographic progression by CT scan and/or bone progression by radionuclide bone scan every 12 weeks

Progressive disease will be considered on the occurrence of the first assessed progression event. For subjects with PSA progression may continue on study drug until radiographic and/or clinical progression, at the discretion of the Investigator and with the Medical Monitor agreement. A treatment diagram for the study is provided below in **Figure 1**.

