### 3.2.2 Clinical Studies

In the Phase I/II trial of GT0918 US 1001, part 1 study of dose escalation, 40 subjects have been treated with GT0918 at seven dose levels: daily 50 mg (n = 3), 100 mg (n = 6), 200 mg (n=6), 300 mg (n=7), 400 mg (n=7), 500 mg (n=6), 600 mg (n=5). All subjects progressed on multiple lines of therapies including, but not limited to, bicalutamide, abiraterone, enzalutamide, docetaxel, cabazitaxel, radium 223, sipuleucel T and pembrolizumab. No DLT has been identified in the planned dose escalation cohorts thus MTD is not defined. GT0918 has been shown generally well tolerated and it has some CTCAE grade 1 and 2 AEs reported, such as fatigue, lethargy, nausea, loss of appetite, anemia, hypercholesterolemia, hyperglycemia, hyperglyceridemia, hot flush, constipation, etc. Three events of 2 grade 3 fatigue, 1 grade 3 anemia, and one event of grade 4 elevated creatine kinase (CK) were reported. Stable disease by imaging scans at 20 weeks by dose group were; 1/50 mg, 1/100mg, 3/400mg, 1/500mg. PSA decreases were also seen among subjects with increasing dosing for a period of time. This is the part II study to further evaluate the safety and tolerability of 2 dosages: 400 and 500 mg in selected subjects with mCRPC progressed on prior treatment either abiraterone or enzalutamide. Early phase 1 study performed in China included 19 subjects who were treated with GT0918 in various doses 50 mg, 100 mg, 200 mg, 300 mg and 400 mg over 3 months. Mild to moderated drug-related AEs were reported, such as hypercholesterolemia, hyperglycemia, hyperglyceridemia, peripheral edema, hot flash, fatigue, nausea, constipation.

Therefore three more clinical trials (China Phase 1 Bioavailability Study, GT0918-CN-1001, GT0918-CN-1002) regarding to GT0918 bioavailability in healthy subject and as a monotherapy drug in mCRPC subjects have finished in China and five on-going GT0918 clinical trials in mCRPC and breast cancer subjects. More information regarding to these trials can be found in investigator brochure.

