## 12.5 Adverse Events

### 12.5.1 Adverse Event Description and Reporting

An adverse event (AE) is any symptom, physical sign, syndrome, or disease that either emerges or, if present at screening, worsens during the study, regardless of the suspected cause of the event. All medical and psychiatric conditions (except those related to the indication under study) present at screening and up until the first dose of study medication will be documented in the medical history eCRF. Worsening of these conditions and newly emerged symptoms, physical signs, syndromes, or diseases should be noted on the AE eCRF during the study.

Progressed disease (PD) and death caused by PD are not AE/SAE and should not be reported on the AE page of the eCRF.

Laboratory test results will be recorded on the laboratory results pages of the eCRF. Laboratory test value abnormalities, if not clinically significant, should not be reported on the AE page of the eCRF as AEs. Clinically significant laboratory abnormalities should be recorded as AEs. Conditions that result from a pre-planned surgical procedure arranged before the subject enrollment, are not considered AE or SAEs if the expected conditions were known before study inclusion. Such medical condition should be reported in the subject's medical history.

Additionally, anticipated AEs for this study population, listed below, must be reported by Investigators to the Medical Monitor but will not be expedited on an individual basis. Instead these AEs will be reviewed in aggregate every 3 months by the Sponsor. This aggregate review may result in an expedited safety report.

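### The ECOG criterion for symptomatic progression names no cause, which makes it easier for disabling toxicity to be attributed to progression and lost from the safety counts by dose

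*Combined protocol and SAP*

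**What the plan says.** Section 13.4, item 4, opens: "Symptomatic progression is defined as evidence of unequivocal symptomatic or clinical progression defined by at least 1 of the following". The listed criteria differ in how they treat cause:

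- Pain: "A marked escalation in cancer-related pain that is assessed by the Investigator", with confirmation at least 3 weeks later.
- Intervention: a need for new anticancer treatment, or "surgical or radiological intervention for complications due to tumor progression".
- Performance status: "A marked deterioration in ECOG performance status to Grade 3 or higher, or".

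The Synopsis (Study Design) names clinical assessment as one of three ways to assess progression, beside PSA and imaging, and adds: "Progressive disease will be considered on the occurrence of the first assessed progression event".

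On reporting, section 12.5.1 says: "Progressed disease (PD) and death caused by PD are not AE/SAE and should not be reported on the AE page of the eCRF". Later in the same section, disease progression is given as an example of what should not be reported. Section 12.5.2 says: "Hospital admission or death caused by progressive disease will not be considered an SAE and do not require expedited reporting". It also says that a serious report already filed for a sign or symptom is likely to be withdrawn once PD is the final diagnosis behind it.

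Section 13.6 bases the safety assessment on AE incidence, AEs leading to discontinuation, and SAEs at each dose level. Section 7.3 lists PD and unacceptable toxicity as separate reasons for withdrawal.

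**The concern.** The main question of the trial is tolerability at 400 mg and 500 mg and the choice of a recommended dose (sections 4.1 and 5.1). The most disabling toxicities are the ones that could take a subject from the entry level of ECOG 0-1 to ECOG 3. If such a decline is entered as symptomatic progression, the reason for stopping can become PD rather than toxicity, and a related serious report can be withdrawn.

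The arm concerned would then show fewer AE discontinuations and SAEs and more clinical progression. The study is open-label and has no data monitoring committee (sections 8.4 and 13.8), so neither blinding nor an independent committee would catch this. With 30 subjects per arm, a few moved cases could matter to the comparison of doses.

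**Working it through.** **Step 1: is the ECOG criterion sufficient, and is it attributed?** One criterion is enough. Of the three set out above, only the ECOG one has no link to cancer, no confirmation and no exclusion of drug toxicity or intercurrent illness. Appendix 1 (section 16.2) defines ECOG 3 by function alone: limited self-care, and in bed or a chair for more than half of waking hours. Table 2 in section 12.5.1 defines a grade 3 AE as one that prevents normal daily activity. The two descriptions can fit the same subject.

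**Step 2: does it lead to PD?** The Synopsis counts the first progression event by any of the three methods, and clinical assessment is one of them. It does not cite section 13.4, so treating item 4 as the definition of clinical progression is a reading. It is the natural one, because item 4 says that it defines symptomatic or clinical progression.

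**Step 3: what leaves the safety data?** PD itself, and admissions and deaths caused by PD. The underlying fatigue or hepatic failure is not excluded. It is lost only if it is attributed to PD.

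**Step 4: how large could this be?** The plan gives no rate for ECOG 3 declines, so only the rate of candidate toxicities can be bounded. The plan's own figure reproduces: 19/958 = 1.98%, stated as 2.0% (section 3.2.3). For phase I, section 3.2.2 says: "Three events of 2 grade 3 fatigue, 1 grade 3 anemia, and one event of grade 4 elevated creatine kinase (CK) were reported", in 40 subjects.

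Expected number = n × p. Chance of at least one = 1 − (1 − p)^n. For example, 60 × 0.05 = 3.0 and 1 − 0.95^60 = 0.954.

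| Candidate event | Rate p | Expected in 60 | At least one in 60 | At least one in 30 |
|---|---|---|---|---|
| Grade 3 fatigue, section 3.2.2 | 2/40 = 5% | 3.0 | 95% | 79% |
| Grade 3 fatigue, section 3.2.3 | 2/100 = 2% | 1.2 | 70% | 45% |
| Drug-related grade 3-4 hepatotoxicity | 19/958 = 1.98% | 1.2 | 70% | 45% |
| Hepatic failure | 2/958 = 0.21% | 0.13 | 12% | 6% |

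Assumptions:
- The two fatigue events were in different subjects.
- The section 3.2.3 denominator, given only as more than one hundred subjects, is taken as 100.
- The two hepatic failures share the denominator of 958.

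One case moved from AE to PD changes an arm's rate by 1/30 = 3.3 percentage points.

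**The case against.** The case on the other side is substantial.

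- **The opening of the definition.** It requires unequivocal progression. A decline that the investigator blames on the drug is hard to call that. This restrains a careful investigator, but the listed criterion still suffices as written, and nothing says how to classify a toxicity-driven decline.
- **The narrow exclusion.** A reader might infer that severe fatigue or hepatic failure is barred from AE reporting. The documents do not support that. Section 12.5.1 defines an AE whatever its suspected cause, and it lists fatigue, anemia, liver injury and hepatic failure among anticipated events that must go to the Medical Monitor. Withdrawal of a serious report under section 12.5.2 applies only when PD is the final underlying diagnosis. This point stands: a loss needs a misattribution.
- **Other safeguards.** Disabling related toxicity leads to interruption, which must be reported (section 8.6.3), so it would often be documented before ECOG 3 is reached. There is a safety review every cycle (section 8.2). An event is serious if either the sponsor or the investigator thinks so (section 12.5.2). Laboratory results are summarised by dose (section 13.6), so liver toxicity remains visible there. These reduce the risk, but they do not restore a discontinuation or SAE that has been recorded as PD.
- **Efficacy.** A reader might infer that efficacy is biased as well as safety. The secondary objectives in section 4.2 are radiographic, PSA and biomarker measures, and none is stated to use ECOG. Section 13.4 also evaluates symptomatic progression by type, which would show part of the problem.
- **The 95% figure.** A reader might take it as the chance of a misclassified case. It is the chance of at least one grade 3 fatigue event at the higher of two rates. That rate comes from phase I subjects treated at 50 to 600 mg, whose prior therapies included docetaxel and cabazitaxel. Prior chemotherapy is an exclusion here (section 7.2).

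**Conclusion.** The gap is real but limited. The ECOG criterion lacks the attribution that the pain and intervention criteria carry. Combined with the PD exclusions and the withdrawal of serious reports, it makes it easier for disabling toxicity to be attributed to PD and to leave the SAE and AE-discontinuation counts by dose. The effect falls on those counts and on clinical PD, not on rPFS, objective response or the PSA endpoints. The documents do not show that toxicity will be lost, only that the wording permits it after a misattribution.

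The figures in the table are ceilings on candidate events under the stated assumptions. The share reaching ECOG 3, and the share then labelled PD, are not given and cannot be derived. This is a low-cost improvement to a trial whose primary question is tolerability. It does not undermine the design.

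**What to change.** 1. **Section 13.4, item 4.** Add to the ECOG criterion that the decline is judged to be due to prostate cancer and not to study drug or intercurrent illness. Record that attribution in one eCRF field. The list also ends with a general statement that performance status will be assessed, which is not a criterion and should be moved out.
2. **Sections 12.5.1 and 12.5.2.** State that when PD is declared on symptoms or ECOG without PSA or imaging progression, the underlying sign or symptom stays on the AE/SAE record with its grade and causality, and the report is not retracted.
3. **Section 13.6.** Tabulate by arm, beside AE discontinuations, the progressions declared on symptoms or ECOG only and all on-study deaths whatever the attributed cause.

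The cost is protocol wording, one eCRF field and one table. There would be slightly fewer clinical progression events and a few more AE records. Attribution remains an investigator judgement. The second and third changes help here because they keep the event visible even when that judgement is wrong.
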